2.3 Rationale

Based on the clinical and preclinical data described above, we propose a prospective phase 1-2 clinical trial that will test the hypothesis that TGF β inhibition using fresolimumab will reduce the development of pulmonary fibrosis after SABR for early stage NSCLC. Thousands of patients per year with early stage NSCLC are treated with SABR and all would benefit from the knowledge gained from this. If successful, the addition of fresolimumab to SABR could increase the ease and speed with which local recurrence can be diagnosed, increasing the chance that additional local therapy could be used for salvage. Additionally, proving that TGF β inhibition can reduce or prevent radiation-induced fibrosis would serve as a proof-of-principle for applying this approach in other cancer types where fibrosis is a significant side effect (eg, head and neck cancer, breast cancer, etc).

2.4 Study Design

Phase 1 component:

Fresolimumab will be on Days 1, 15, and 36 and SABR will be administered at 12.5 Gy/fraction in 4 fractions between Days 8 and 12 to a total of 5 patients who will be evaluated for safety, and additional patients will be enrolled if specific AE's are observed. A dose reduction may be implemented if excessive toxicity is observed.

Blood would be collected for pharmacokinetic studies (only Phase 1). This is a single-arm, open-label study

Phase 2 component:

Up to a total of 60 patients, including the Phase 1 portion. Fresolimumab will be administered IV at the dose selected in the preceding Phase 1 (3 mg/Kg) component on Days 1, 15 (+ 6 days), and 36 (+/- 6 days) and SABR (-1/+5 days) will be administered at 12.5 Gy/fraction in 4 fractions between Days 8 and 12.

This is a single-arm, open-label study conducted under IND 125981 (Sponsor-Investigator/ IND Holder: [name], PhD).

3. PARTICIPANT SELECTION AND ENROLLMENT PROCEDURES

3.1 Inclusion & Exclusion Criteria

Inclusion Criteria:

1. Newly diagnosed, histologically-proven T1-T2bN0M0 (Stage IA-IIA) NSCLC, with maximum tumor diameter ≤ 5 cm under consideration for stereotactic ablative body radiotherapy (SABR) as definitive primary treatment
2. Patient judged to be inoperable or at high surgical risk by a board-qualified thoracic cancer surgeon who has evaluated the subject within the prior 12 weeks, or the patient's case has been discussed at a multidisciplinary tumor board with a thoracic cancer surgeon in attendance, or a patient who refuses surgery or declines to be evaluated for surgery within 12 weeks
3. ECOG PS 0 to 2
4. Age greater than or equal to 18 years old and able to give informed consent
5. Men or women of child-bearing potential must agree to use an acceptable method of birth control (hormonal or barrier method of birth control; abstinence) to avoid pregnancy for at least 90 days after last study treatment (radiation or fresolimumab)

Exclusion Criteria:

1. Significant anemia (hemoglobin below 9.0 g/dL) or neutropenia ($ANC < 1000/mm^3$)
2. Prior history of multifocal adenocarcinoma in situ (ie, classic or pure bronchioloalveolar carcinoma)
3. Prior history of keratoacanthoma (well-differentiated squamous cell skin cancer variant, often centrally ulcerated). History of basal cell cancer is allowed.
4. Pre-malignant skin lesion(s) noted on prescreening skin exam, except for actinic (solar) keratosis
5. Prior radiotherapy overlapping with high dose region of planned SABR course
6. Prior history of head and neck; oral; or bladder cancer
7. Prior receipt of systemic treatment (chemotherapy, targeted therapy, or immunotherapy) for the lesion under consideration of treatment
8. Uncontrolled, inter-current or recent illness that in the investigator's opinion precludes participation in the study, including those undergoing therapy for a separate invasive malignancy
9. Contraindication to receiving radiotherapy

10. Known allergy to components of fresolimumab
11. Pregnant or breastfeeding. All women of child-bearing potential (last menstrual period within the previous 12 months and not surgically sterile) will be tested for pregnancy at pre-entry.

3.2 Informed Consent Process

All participants will be provided with a consent form describing the study with sufficient information for participants to make an informed decision regarding their participation. Participants will sign the IRB approved informed consent prior to participation in any study specific procedure. The participant will receive a copy of the signed and dated consent document. The original signed copy of the consent document will be retained in the medical record or research file.

3.3 Randomization Procedures

Phase 1: Single-arm, non-randomized

Phase 2: Single-arm, non-randomized

3.4 Study Timeline

Estimated study length: 6 years consisting of 5 year(s) accrual + 1 year follow-up

Primary Completion (for CT.gov):

The study is expected to reach primary completion approximately 72 months from the time the study opens to accrual

Study Completion:

The study is expected to reach study completion approximately 72 months from the time the study opens to accrual. Phase 1 is expected to be completed in approximately 18 months, and phase 2 in approximately 36 months

4. TREATMENT PLAN

4.1. Pre-treatment tests

The following will be completed prior to treatment (for specifics see study calendar):

[figure not shown]
- a) Medical history and clinical examination, including a full skin exam by the investigators.
- b) Laboratory testing
- c) Baseline imaging- Acceptable to use simulation scans.
- d) Signed informed consent document.

4.2. Drug Therapy

4.2.1 Fresolimumab Administration

Fresolimumab will be administered IV at a dose of 3 mg/kg on Days 1, 15, and 36, with SABR (-1/+5 days) being administered at 12.5 Gy/fraction in 4 fractions between Days 8 and 12.

Administration Schema:

** -1/+5 days to allow for weekends and holidays and unforeseen circumstances

* +/- 6 days to allow for weekends and holidays and unforeseen circumstances

Phase 1 (see study Schema, pg 9):

We will enroll 5 patients at 3 mg/kg of fresolimumab.

Dose limiting toxicity (DLT) is defined as the following grade 3; 4; or 5 CTCAE v4 events determined to be of possibly; probably; of definite relationship to treatment; occurring after 1st dose of fresolimumab and up to 30 days after the last dose of fresolimumab:

- 1) Radiation pneumonitis, or
- 2) Bronchopulmonary hemorrhage

Of the 5 patients, if none experience DLT, then 3 mg/kg will be the dose for the Phase 2 component.

If one patient experiences DLT, an additional 5 patients will be enrolled at 3 mg/kg. If no more patients experiences DLT, then 3 mg/kg will be the dose for the Phase 2 component. If 2 or more patients experience DLT in the total expanded cohort (or 2 or more patients in the initial cohort experience DLT), then the investigational dose of fresolimumab will be changed to 1 mg/kg. If 2 or more patients in the initial cohort experience DLT before all 5 patients have been enrolled, the remaining patients will receive the lower dose of 1 mg/kg.

At the lower dose (1 mg/kg), 5 more patients will be enrolled. If no more patients experience grade 3 or higher toxicity, then 1 mg/kg will be the dose for the Phase 2 component.

If one or more patients of 5 experience DLT at the reduced dose, the investigators will consider closing the study.

Phase 2:

Fresolimumab will be administered IV at the dose determined from Phase 1 on Days 1, 15 (+ 6 days), and 36 (+/- 6 days), with SABR (-1/+5 days) being administered at 12.5 Gy/fraction in 4 fractions between Days 8 and 12.

4.2.2 General Concomitant Medication and Supportive Care Guidelines

In general, concomitant medications and therapies deemed necessary for the supportive care and safety of the patient are allowed, provided their use is documented in the patient records. Patients must be instructed not to take additional medications including over-the-counter products and herbal/alternative medications during the study without prior consultation with the investigator.

Permitted treatments during the study include, but are not limited to the following:

- Pain medication to allow the patient to be as comfortable as possible
- Nutritional support or appetite stimulants (eg, megestrol)
- Oxygen therapy and blood products or transfusions

The following concomitant treatments are not allowed during the study:

- Concurrent use of other investigational drugs is not permitted.

- The administration of other antineoplastic therapy (eg, chemotherapy, hormone therapy, immunotherapy, targeted therapy, and monoclonal antibodies) is not permitted.

4.2.3 Duration of Therapy

Patients will be seen on Days 1, 15, and 36 when they receive fresolimumab, and will be seen in follow-up at 3rd; 6th; 9th and 12th month from end of SABR completion (+/- 2 weeks). History and physical exam, ECOG PS, toxicity evaluation, CT Thorax (Chest) imaging, and labs will be evaluated at each of these visits. Skin exams will be conducted at the 3rd month from end of SABR completion. PFTs will be completed at 6th and 12th month. PET/CT imaging will be evaluated at 6th month. The duration of the treatment phase of the study will be through the 1st follow-up visit, approximately 90 days after the SABR is completed.

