5.2 Pharmacokinetics

The pharmacokinetics of fresolimumab have been characterized in patients with advanced malignant melanoma and RCC, IPF, and FSGS in Phase 1 trials following single and multiple IV doses ranging from 0.1 mg/kg to 15 mg/kg. Toxicology studies at doses of 0.1 to 50 mg/kg have been conducted in non-human primates and generally have had exposures 10-fold lower than the exposure levels seen with the corresponding dose in humans.

Dose-normalized values of C_{max} were approximately similar among dose groups, regardless of patient disease. Fresolimumab clearance showed no obvious dose-dependent trend, suggesting that the target antigen was not saturated in the studied dose range. The overall terminal elimination half-life is approximately 2 to 3 weeks.

Serum concentrations of fresolimumab from the phase 1 studies were pooled and analyzed using a non-linear mixed-effects modeling procedure. The PK of fresolimumab was best described using a 2-compartment open model with first-order elimination from the central compartment. The evaluation of covariate effects showed an effect of weight as the most important covariate using a full allometric model. Over the range of body weights of 50 to 100 kg, the typical value of clearance changed by no more than 30%. There was no difference in the PK behavior of fresolimumab based on patient disease. No other covariates were identified as being predictive of PK variability.

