7.1.2.1 Skin

Based on the clinical experience to date, the main epithelial adverse reaction to fresolimumab appears to be adverse events involving the skin, most notably keratoacanthoma and squamous cell carcinoma. The development of these lesions appears to be related to both dose and duration of exposure. Because of this potential risk, skin exams, evaluating for treatment emergent lesions such as KA and drug reactions should be performed in all patients receiving fresolimumab. Patients who develop concerning treatment-emergent skin lesions should be referred to a dermatologic oncologist or dermatologist for evaluation within 2 weeks of reported symptoms.

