7.3 Reporting Adverse Events

Adverse events will be graded according to CTCAE v4. Adverse Events will be clearly noted in source documentation and listed on study specific Case Report Forms (CRFs). The Protocol Director (PD) or designee will assess each Adverse Event (AE) to determine whether it is unexpected according to the Informed Consent, Protocol Document, or Investigator's Brochure, and related to the investigation. All AEs will be collected from signing of informed consent through 30 days after last study treatment. Prior to Day 1, only Serious Adverse Events (SAEs, see below) deemed related to study procedures need to be collected. All SAEs will be tracked until resolution, or until 30 after the last dose of the study treatment.

Each occurrence of a given adverse event will be recorded. Use of steroid as treatment for adverse event will be recorded. Only the most severe grade over the course of a given episode will be recorded.

Laboratory events defined as worsening of the laboratory value by one CTCAE v4 (Common Terminology Criteria for Adverse Events, version 4) grade or more from baseline value that meet the regulatory criteria for a serious adverse event (SAE) will be reported.

Note: All deaths due to any cause must be reported immediately (within 24 hours) to Sanofi Genzyme.

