9. STUDY CALENDAR

Parameters	Pre-Entry ⁶	Day 1	Day 8-12 ⁴	Day 15 ⁷	Day 36 ⁸	3 month ^{9,10}	6 month ¹⁰	9 month ¹⁰	12 month ¹⁰
History & Physical Exam	X	X		X	X	X	X	X	X
Complete skin exam ¹	X					X			
ECOG PS	X	X		X	X	X	X	X	X
Labs ²	X	X		X	X	X	X	X	X
CT Thorax (Chest)	X ¹¹					X	X	X	X
PET/CT	X ¹¹						X		
Toxicity evaluation		X		X	X	X	X	X	X
PFT ³	X						X		X
SABR ⁴			X						
Fresolimumab ⁵		X		X	X				

- ¹ To be performed by the investigators. Suspect lesions will be referred for further evaluation to a dermatologic oncologist or dermatologist as appropriate
- ² Includes CBC with differential and complete metabolic panel. Also urine or serum pregnancy test required for women of childbearing potential at pre-entry only
- ³ Including DLCO, FEV1, and FVC
- ⁴ 12.5 Gy/fraction in 4 fractions between Days 8 to 12. Minus 1 to + up to 5 days to allow for weekends and holidays and unforeseen circumstances.
- ⁵ 3 mg/kg IV (or other determined dose from Phase 1) given on days 1, 15, and 36
- ⁶ All pre-entry assessment should be obtained within 4 weeks of enrollment
- ⁷ 3 days after completion of SABR, + up to 6 more days to allow for weekends and holidays and unforeseen circumstances
- ⁸ Target 21 days after dose 2 of fresolimumab. +/- 6 days to allow for weekends and holidays and unforeseen circumstances
- ⁹ Needs to be at least 90 days after completion of SABR for safety analysis
- ¹⁰ +/- 2 weeks to allow for weekends and holidays and unforeseen circumstances. Date counted from completion of SABR.
- ¹¹ Acceptable to use non-diagnostic simulation planning scans for baseline imaging

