Hilar node failure (HNF)	Appearance of tumor in ipsilateral hilar lymph nodes.
Ipsilateral mediastinal nodal failure (MNF)	Appearance of tumor in ipsilateral mediastinal and/or subcarinal lymph nodes.
Distant Failure	
Distant nodal failure (DNF)	Appearance of tumor in ipsilateral supraclavicular or contralateral lymph nodes.
Distant metastatic failure (DMF)	Appearance of tumor deposits characteristic of NSCLC metastasis (chest wall other than incision sites or immediately adjacent to primary, mediastinal structures/diaphragm, malignant pleural effusion/pericardial effusion), contralateral lung and/or other distant sites.

Potential adverse events will be monitored by treating physicians at each follow-up visit, and scored using CTCAE v4 with type and grade.

Post-treatment changes in pulmonary function will be evaluated by changes in pulmonary function test at enrollment, 6-month, and 12-month follow-up.

Recurrence rate is determined by time from study enrollment to first documented date of recurrence.

Progression-free survival (PFS) is time from time from study enrollment until the first documented date of disease progression.

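### Section 7.3 ends adverse event collection 30 days after last treatment, before the month 3 to 12 toxicity evaluations and the only post-baseline complete skin exam

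*Combined protocol and SAP*

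**What the plan says.** **The collection rule.** Section 7.3: "All AEs will be collected from signing of informed consent through 30 days after last study treatment". Inclusion criterion 5 treats study treatment as either radiation or fresolimumab, so on schedule the last treatment is fresolimumab dose 3.

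**The provisions that look further.**
- Section 4.2.3: "The duration of the treatment phase of the study will be through the 1st follow-up visit", about 90 days after SABR. The same section lists a toxicity evaluation at every follow-up visit.
- Section 9: toxicity evaluation is marked at months 3, 6, 9 and 12. Footnote 9 says of the month 3 visit: "Needs to be at least 90 days after completion of SABR for safety analysis".
- Section 10.2: "Potential adverse events will be monitored by treating physicians at each follow-up visit", with CTCAE v4 type and grade.
- Section 7.12: crude rates of severe (grade 3 or worse) radiation pneumonitis and bronchopulmonary hemorrhage are reviewed once 25 patients have six months of follow-up.

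**Skin.** Section 7.1.2.1 names keratoacanthoma and squamous cell carcinoma (SCC) as the leading skin reactions and adds: "The development of these lesions appears to be related to both dose and duration of exposure". In Section 9, "Complete skin exam" has its own row, marked at pre-entry and month 3 only. Section 4.2.3 agrees: "Skin exams will be conducted at the 3rd month from end of SABR completion". The pre-entry exam precedes every dose; no post-baseline complete skin exam is scheduled before doses 2 and 3.

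**Use of the data.** AE scoring is a secondary endpoint in both phases (Section 12.4), and AEs are to be tabulated by organ system and severity (Section 12.4.2).

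**The concern.** Section 7.3 is the sentence that defines which AEs enter the record, and it closes before any of the four post-SABR follow-up visits. Two coordinators could each follow the protocol and treat the same month 3 finding differently: one enters it because Section 10.2 says to score it, the other leaves it out because Section 7.3 has closed. The AE table could then be incomplete, or inconsistent between patients, with nothing in the output to show it.

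Skin is where this shows most plainly, because the one post-baseline exam designed to find the drug's characteristic lesions comes after collection has closed. Section 7.12 leaves keratoacanthoma and skin SCC out of the enrollment-pause count, so for lesions not classed as serious the AE record is the main place they would be counted. The Section 7.12 toxicity review has the same difficulty: it uses events from a period that the collection rule does not cover.

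**Working it through.** The plan gives no figure to reproduce. The check is day arithmetic, counted from SABR completion.

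**Inputs (Section 9 footnotes and Section 7.3).**
- Dose 2: 3 to 9 days after SABR completion (footnote 7).
- Dose 3: 21 ± 6 days after dose 2 (footnote 8).
- Month 3 exam: ± 2 weeks, but not before day 90 (footnotes 9 and 10). Taking 3 months as 91 days, the range is 90 to 91 + 14 = 105.
- Window close: dose 3 + 30 days.

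**Gap = exam day − (dose 3 day + 30).**

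| Dose 3 | Days after SABR | Window closes | Gap, exam at day 90 | Gap, exam at day 105 |
|---|---|---|---|---|
| Earliest | 3 + 15 = 18 | 48 | 42 | 57 |
| Nominal | 3 + 21 = 24 | 54 | 36 | 51 |
| Latest | 9 + 27 = 36 | 66 | 24 | 39 |

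The gap runs from 24 to 57 days. In study days, the nominal case is: SABR ends Day 12, dose 3 is Day 36, the window closes on Day 36 + 30 = 66, the exam is Day 12 + 90 = 102, and the gap is 36 days.

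**Sensitivity.**
- Dropping the 90-day floor puts the earliest exam at 91 − 14 = 77 days; the smallest gap is 77 − 66 = 11 days.
- Treating the windows as fixed study days and stacking the extremes (SABR ends Day 10, dose 3 on Day 48), the gap is (10 + 90) − (48 + 30) = 22 days with the floor and (10 + 77) − 78 = 9 days without it.
- If dose 3 is skipped under Section 6, the window closes 33 to 39 days after SABR. The gap is then 90 − 39 = 51 to 105 − 33 = 72 days (nominally 102 − 45 = 57).

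No in-window schedule puts the month 3 exam inside the Section 7.3 window.

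**Later visits.** At 30.44 days per month from Day 12, months 6, 9 and 12 fall on about Days 195, 286 and 377. These are 129, 220 and 311 days after Day 66. The six-month data behind the Section 7.12 review therefore extend about 129 days past the close.

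**Drug still present at the close.** Section 5.2: "The overall terminal elimination half-life is approximately 2 to 3 weeks". Thirty days is 30/21 = 1.4 to 30/14 = 2.1 half-lives, leaving 0.5^1.43 = 37% to 0.5^2.14 = 23% of the terminal-phase level. This approximation ignores the distribution phase. It shows that the cut-off does not mark the end of exposure; it does not estimate any missed events.

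**The case against.** **The specific provisions should govern.** Toxicity evaluation sits in the same month 3 column as the skin exam, Section 4.2.3 repeats it, Section 10.2 requires scoring, and footnote 9 ties the visit to safety. Sensible staff would record a month 3 lesion. This has force: the documents show a contradiction, not demonstrated data loss. But the protocol gives no order of precedence, and the sentence on the other side is the explicit collection rule.

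**The most important lesions have another route.** A reader might infer that skin cancers found at month 3 go unreported. The documents do not support that. Section 7.4 gives invasive or malignant cancer as an example of a serious event, exclusion criterion 3 describes keratoacanthoma as a variant of squamous cell skin cancer, and Section 7.5 requires related serious events to be reported whenever they come to light. The exposed remainder is lesions judged non-serious or unrelated, lesser skin reactions, and other non-serious AEs found at months 3 to 12.

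**Exam frequency.** A reader might also infer that patients receive doses 2 and 3 without any skin check, or that complete exams on Days 15 and 36 are needed. The pre-entry exam comes before all dosing, and both visits include a physical exam and a toxicity evaluation. No document gives a lesion rate after one or two doses. With only three doses and a risk tied to cumulative exposure, one exam after full exposure is defensible. Extra exams would be a preference.

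**Conclusion.** The contradiction stands. Section 7.3 closes AE collection nominally on Day 66, while Sections 4.2.3, 9, 10.2 and 7.12 presuppose toxicity data to month 6 or month 12. The only post-baseline complete skin exam falls after the close under every allowed schedule, by 24 to 57 days on the footnotes. The figures assume a 91-day three-month interval and dose 3 given in window; skipping dose 3 widens the gap.

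If Section 7.3 is followed literally, non-serious late AEs drop out of a planned secondary endpoint and its table. How many is unknown, because the documents give no event rates for that period. The dose-limiting toxicity assessment is unaffected, since Section 4.2.1 uses its own limit of 30 days after the last dose. The phase 2 primary endpoint rests on CT scoring and is also unaffected. Extending collection only to month 3 would not remove the conflict, because the month 6, 9 and 12 evaluations would remain outside it.

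**What to change.** Amend Section 7.3 so that AEs found at the scheduled toxicity evaluations are collected and tabulated through the month 12 visit. This brings it into line with Sections 4.2.3, 9, 10.2 and 7.12.

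If that is judged too much, the minimum is:
- all AEs, including keratoacanthoma and skin SCC, through month 3; and
- radiation pneumonitis and bronchopulmonary hemorrhage of grade 3 or worse through month 6.

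Under the minimum, Sections 9 and 10.2 should also say that later toxicity findings outside those categories are not part of the AE table.

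The cost is an edit to one sentence and slightly more data entry. The visits and evaluations already exist, so no procedure or staff is added. Reported AE rates may rise slightly. No change to the Day 15 or Day 36 examinations is required.
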